9. RESEARCH METHODS

9.1 STUDY DESIGN

A retrospective analysis will be done based on a claims dataset delivered by two German sickness funds (so far, a cooperation with [REDACTED] is planned, second sickness fund needs to be named yet). The dataset will cover the period 01/01/2013-30/06/2018⁷. In selected analyses, incident COPD patients will be observed for an exact follow-up period of 12 months (in subgroup analyses: 24 and 36 months); censoring of patients will only be done in case a patient died during the respective follow-up period. [REDACTED]

The data will be analyzed for a pre-index period (12 months before index diagnosis) and for a follow-up period of 12 months after index date. In subgroup analyses, longer follow-ups (24 and 36 months, and full observation time (up to 54 months⁸)), are used. Death after index diagnosis during the follow-up is the only accepted exception from this rule. For a subsample of patients, disease management program (DMP) data might be available. These provide disease specifics such as forced expiratory volume in 1 second (FEV₁) values, specifics of prescribed therapy, and exacerbation frequency and severity.

The dataset contains available information on the sociodemographic characteristics of the patients, their treatment with prescription aids and medications, their outpatient and inpatient treatment, and COPD-specific clinical parameters for the patients who participated in a disease management program (DMP). A first overview of data generally available in claims data of a German sickness fund is given in Table 1. The study-specific data set (required data according to approved study protocol) needs to be approved by the respective sickness funds, based on the study objectives and the respective methodology as outlined in this protocol.

⁷ If more data will be available until time of analysis start, further quarters (from 2018) will be included into the analysis.

⁸ If more data will be available until time of analysis start, further quarters (from 2018) will be included into the analysis.

[figure not shown]
Table 1 Data generally available in the claims data set

Sociodemographic characteristics	Inpatient care	Outpatient care	Outpatient medication (prescriptions only)	Other data

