9.2 SETTING

An anonymized dataset from the cooperating sickness funds, which includes all patients with at least one COPD diagnosis, who were insured by this sickness funds for the entire period (01/01/2013 - 30/06/2018) will be available.

A patient will be confirmed as being COPD-incident if specialists documented at least two confirmed outpatient COPD diagnoses (ICD J44.-) and/or at least one inpatient COPD diagnosis (ICD J44.-), without such diagnoses in the previous 12 months and without any COPD prescription in the previous 12 months (Suppl. Table 2).

Specific inclusion criteria can be described as follows:

- All patients should have been covered by the sickness fund for the entire period (01/01/2013-30/06/2018) or, in case a patient deceased after index date, for the time until death
- A patient will be included as an incident COPD patient if either a hospital documented at least one COPD diagnosis (ICD-10 J44.-) or a specialist (pneumologist) documented at least two confirmed COPD diagnoses (above ICD-10 code) in two different quarters; the first of the above diagnoses is defined as index diagnosis; inclusion period is defined as lasting from 01/01/2014 until 30/06/2017

- Patients should not have received any COPD diagnosis (ICD-10 J44.-) or any COPD-associated medication (Suppl. Table 2)⁹ in the 12 months pre-index period
- Patient should have, at date of incident COPD diagnosis (index date), an age of at least 40 years

Patients who received at least one confirmed inpatient asthma diagnosis or two confirmed outpatient diagnoses of asthma (ICD-10: J45.-) by pneumologists after the incident COPD diagnosis (index diagnosis) will be separately observed.

Based on these inclusion/exclusion criteria, the following data sets will be analyzed (Figure 3)¹⁰:

- COPD-FULL DATA: All incident COPD patients with a follow-up of up to 54 months
- COPD-12: All incident COPD patients with a follow-up¹¹ of 12 months since index date
- COPD-24: All incident COPD patients with a follow-up of 24 months since index date
- COPD-36: All incident COPD patients with a follow-up of 36 months since index date
- COPD DMP-FULL DATA: All incident COPD patients with available DMP data (at least one entry during 3 months after index date¹²) and a follow-up of up to 54 months.
- COPD DMP-12: All incident COPD patients with available DMP data (at least one entry during 3 months after index date) and a follow-up of 12 months since index date

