- COPD DMP-24: All incident COPD patients with available DMP data (at least one entry during 3 months after index date) and a follow-up of 24 months since index date
- COPD DMP-36: All incident COPD patients with available DMP data (at least one entry during 3 months after index date) and a follow-up of 36 months since index date.

⁹ Prescription of systemic/oral corticosteroids (SCS/OCS) will not be considered as exclusion criteria

¹⁰ Please note that this samples will not include patients with at least one confirmed inpatient or two confirmed outpatient diagnoses of asthma (ICD-10: J45.-) by pneumologists after the incident COPD diagnosis (index diagnosis) during the follow-up period. Those patients will be described separately.

[figure not shown]
¹¹ Time since patient-individual index date until 30/06/2018; patients who died within this period will not be excluded from the analysis

¹² So far it is unknown how many patients were included in the DMP directly after incident diagnosis and for how many patients an entry in the first months after diagnosis will be available. Thus, depending on the pattern that will be observed in the data, the restriction „at least one entry during the 3 months after index date“ might be extended to „at least one entry during the 6/12 months after index date“.

Figure 3

Baseline period, inclusion period, follow-up period for different study samples

(note: for time to event analyses, COPD-full data sample (with full follow-up times) will be applied). DMP: disease management program (refers to the subsample of patients who participate in the COPD DMP and thus provide more detailed data)

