¹³ Even if this study is based on fixed follow-up periods, death of some patients during the follow-up period might lead to shorter follow-up periods than 12, 24, or 36 months in some patients. That is why above numbers will be reported per observed patient year.

¹⁴ Analyses will be done for all three defined follow-up periods (12 months, 24 months, 36 months). For major treatment patterns, characteristics of respective patients will be described.

¹⁵ Switching between different drugs of the same drug class (LAMA,LABA,ICS) will not be taken into account for this analysis.

Table 2 (cont'd)

Description of treatment patterns/cascades (template for reported outcomes)
 (please note: below table might not show all theoretically possible treatment patterns. In the analysis, based on observed treatment patterns, all treatment pattern combinations that were observed in >5% of the patient population will be reported)

Therapy pattern after index date	1st line	2nd line	3rd line	4th line	N (%) of patients
Mono, with switch to dual therapy	LAMA	LAMA+LABA	-	-	...
		LAMA+ICS			
		LABA+ICS			
	LABA	LAMA+LABA		-	
		LAMA+ICS			
		LABA+ ICS			
Mono, with switch to dual therapy and subsequent switch to another dual therapy	LAMA	LAMA+LABA	LAMA+ICS		
		LAMA+ICS	LAMA+LABA		
		LABA+ICS	LABA+ICS		
	LABA	LABA+LAMA	LABA+ICS		
		LABA+ ICS	LABA+LAMA		
		LAMA+ICS	LAMA+ICS		
Mono, with switch to dual therapy and subsequent triple therapy	LAMA	LAMA+LABA	LAMA+LABA+ICS	-	...
		LAMA+ICS	LAMA+LABA+ICS		
	LABA	LAMA+LABA	LAMA+LABA+ICS	-	
		LABA+ ICS	LAMA+LABA+ICS		
Mono, with switch to triple therapy	LAMA	LAMA+LABA+ICS			
	LABA	LAMA+LABA+ICS			

Table 2 (cont'd)

Description of treatment patterns/cascades (template for reported outcomes)
 (please note: below table might not show all theoretically possible treatment patterns. In the analysis, based on observed treatment patterns, all treatment pattern combinations that were observed in >5% of the patient population will be reported)

Therapy pattern after index date	1st line	2nd line	3rd line	4th line	N (%) of patients
Dual therapy, no switch during follow-up period	LAMA+LABA LABA+ICS LAMA+ICS	- - -	- - -	- - -	...
Dual therapy with switch to another dual therapy	LAMA+LABA LAMA+ICS LABA+ICS	LAMA+ICS LAMA+LABA LAMA+ICS	LAMA+LABA LAMA+ICS		
Dual therapy with switch to triple therapy	LAMA+LABA LAMA+ICS LABA+ICS	LAMA+LABA+ ICS LAMA+LABA+ ICS LAMA+LABA+ ICS	-		
Triple therapy, no switch during follow-up period	LAMA+LABA+ICS				

Table 2 (cont'd)

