Health care resource use (HCRU) and direct cost will be reported as described in Table 3, based on the perspective of a German sickness fund and based on prices of the respective years as reported in the claims data base. HCRU and cost will be reported for the following samples in separate analyses: COPD-12, COPD-24, and COPD-36.

Generally, HCRU/cost will be reported per observed patient year. HCRU and cost will be compared between the following patient groups:

- Patients participating in a DMP versus those who did not participate
- Patients having received early (first 3 months after index date) a triple combination therapy (LABA+LAMA+ICS) versus those who did not.

[figure not shown]
In a separate analysis based on COPD-36 sample, cost during the first year after incident COPD diagnosis will be compared with costs in the second and third year after incident diagnosis.

[figure not shown]
[figure not shown]
Table 3 HCRU and direct healthcare cost definition

Item	HCRU	Cost
COPD medication	
• Nb. of prescriptions for medications as reported in Suppl. Table 2, per agent type• Nb. of prescribed DDDs for medications as reported in Suppl. Table 2, per agent type	
• Drug cost (based on list prices) for medications as reported in Suppl. Table 2.
Other medications	
• Nb. of non COPD-medications, defined as at least 2 prescriptions of an agent (on third level of ATC groups)• Antibiotics for systemic use (ATC J02AA) and antibiotics in combination with corticosteroids (ATC D07C)	
• Drug cost of prescribed non-COPD medications
Outpatient treatment	
• Nb. of GP visits• Nb. of pneumologist visits• Nb. of other outpatient specialist visits	
• Cost of outpatient visits as defined in the HCRU column, based on the proxy of “treatment points”
Hospitalizations	
• Nb. of hospitalizations with a COPD-exacerbation (J44.1) including mean duration of stay in days• Nb. of hospitalizations with any COPD diagnosis as main diagnosis (J44.-) including mean duration of stay• Other non-COPD hospitalizations including mean duration of stay in days• Time to first all-cause hospitalization	
• Cost for hospitalizations as defined in the HCRU column

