9.7 DATA ANALYSIS

9.7.1 Main analysis

Generally, for all analyses specific samples will be used; these have been defined further above. Mainly, descriptive statistics will be applied in this study. Descriptive analysis of the data will be performed using summary statistics for continuous and categorical data. Continuous data will be described by the number of non-missing values, median, mean, range, standard deviation and 95% confidence intervals (CIs). Frequency tables will be generated for categorical data. Selected continuous variables will be categorized in a clinically meaningful way.

For rates/frequencies related to time periods, that might vary between the patients (e.g. shorter follow-up period due to death), respective numbers will be reported per patient-year (PY).

Furthermore, time-to-event analyses (Kaplan-Meier curves) will be conducted whenever applicable and appropriate. Especially, for the ██████████ KM curves will be evaluated.

Comparisons for categorical variables will be conducted using either Chi-square tests or Fisher's exact test (when the values in any of the cells of a contingency table are below 5). For continuous variables, statistical comparisons will be conducted using t-test or a suitable non-parametric test (for variables with skewed distribution).

The main analyses planned are summarized in Table 5.

Table 4 Overview of main planned analyses

Endpoint/study objective	Time period	Main reporting/analyses
PRIMARY: Description of drug treatment of incident COPD patients	Different follow-up periods since index date	Descriptive statistics (categorical variables: frequencies/percentages; continuous variables: mean, SD, median, ranges and 95% CIs) Comparisons for categorical variables: either Chi-square tests or Fisher's exact test; Comparison for continuous variables: t-test or a suitable non-parametric test Analysis of time to escalation therapy (therapy including ICS) using KM methodology

Table 4 (cont'd)

Overview of main planned analyses

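### The COPD-36 comparison of first-year with later-year cost mixes real change with calendar-price change and with the loss of patients who die

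*Combined protocol and SAP*

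**What the plan says.** The third secondary objective (protocol section 9.3.2.2) describes health-care resource use and direct cost. After two between-group comparisons (disease management programme or not, early triple therapy or not), it adds a separate analysis in COPD-36: "cost during the first year after incident COPD diagnosis will be compared with costs in the second and third year after incident diagnosis". Four other statements govern that analysis.

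- **Prices.** Resource use and cost are reported from the sickness-fund perspective and "based on prices of the respective years as reported in the claims data base". No common price year is named.
- **Scale.** "Generally, HCRU/cost will be reported per observed patient year". Whether this means total cost over total patient-years or the average of individual rates is not stated.
- **Sample and deaths.** The sample is "COPD-36: All incident COPD patients with a follow-up of 36 months since index date". Footnote 11 in section 9.2 adds that "patients who died within this period will not be excluded from the analysis", and footnote 13 in section 9.3.2.1 accepts that "death of some patients during the follow-up period might lead to shorter follow-up periods than 12, 24, or 36 months in some patients".
- **Tests.** Section 9.7.1 says "For continuous variables, statistical comparisons will be conducted using t-test or a suitable non-parametric test", the latter for skewed variables. The third-secondary row of Table 4 names the same family. Neither place says paired or unpaired, and no test is named for the year-by-year comparison itself.

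**The concern.** In the two between-group cost comparisons, both groups are spread over broadly the same calendar period, so price changes largely cancel. Here they do not. Every patient's third year starts two calendar years after the first, whatever the index date. At nominal prices, price change is fully confounded with time since diagnosis, and a larger sample does not remove it.

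The patients compared also change. Year 1 includes everyone. Year 2 includes only those alive at its start, and year 3 only those alive at its start. Dividing by observed patient-years corrects for how long people were observed, not for who remains. If patients who die early are costlier, later years look cheaper even when no individual's cost has moved.

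Section 7 says the results could serve as a basis for managed-care projects with payers, and section 12 says they will be published. A reader could take price drift or survivor loss for a change in the cost of the disease.

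**Working it through.** The protocol gives no correlation, standard deviation, mortality or price-growth figure for this comparison, so there is no stated result to reproduce. Every rate below is an assumption, shown as a range.

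1. **Size of COPD-36.** The inclusion period, 01/01/2014 to 30/06/2017, is 42 months. A possible 36 months before 30/06/2018 needs an index date by about 30/06/2015, which covers 18 of those months. With uniform incidence, 18/42 = 43%, and 0.43 × 40,000 is about 17,000 patients. Precision is therefore not the main problem.

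2. **Price drift.** With growth g a year, year 3 against year 1 is inflated by (1+g)² − 1. For g = 1% this is 1.01² − 1 = 2.0%; for g = 3% it is 1.03² − 1 = 6.1%. For the mean of years 2 and 3 the inflation is [(1+g) + (1+g)²]/2 − 1, which gives 1.5% and 4.5%.

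3. **Loss of sicker patients.** A cohort of 400,000 was simulated in which each patient's cost rate is constant over time. Frailty is gamma with mean 1 and variance 1, the death hazard is proportional to frailty, and cost is proportional to the square root of frailty. Cost per patient-year is total cost over total patient-years in each year.

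| Annual mortality at average frailty | Year 3 / year 1, no end-of-life cost | Year 3 / year 1, high end-of-life cost |
|---|---|---|
| 3% | 0.97 | 0.96 |
| 5% | 0.95 | 0.94 |
| 8% | 0.93 | 0.90 |
| 10% | 0.91 | 0.87 |

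   High end-of-life cost means an extra three times the patient's annual cost, spread over the last three months of life.

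4. **Both together.** For patients whose real cost is flat, the extremes of steps 2 and 3 multiply to 1.0201 × 0.872 = 0.89 and 1.0609 × 0.971 = 1.03. The reported change could therefore run from an 11% fall to a 3% rise.

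5. **Pairing.** With equal SDs and correlation ρ between years, the unpaired standard error over the paired one is 1/√(1−ρ). For ρ = 0.3 this is 1/√0.7 = 1.20; for ρ = 0.6 it is 1/√0.4 = 1.58. If the first-year SD were twice the later one, the ratio would be √(5/(5−4ρ)), that is 1.15 to 1.39.

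6. **Choice of estimator.** In the same simulation, averaging individual rates instead of dividing totals raises yearly levels by 1% to 2% without end-of-life cost, and by 18% to 48% with high end-of-life cost. Short observation before death drives the difference.

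**The case against.** The case on the other side has four parts.

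- **Nominal prices are a declared choice.** They show what the fund paid, and no passage says that prices rose. Drug cost uses list prices and outpatient cost a proxy based on treatment points, so one growth rate need not fit every component. This stands against any fixed size or sign of the drift. It does not remove the confounding with time since diagnosis.
- **Cost per patient-year among those alive in each year is a legitimate descriptive quantity for a payer.** This also stands, and it is why that quantity should remain the main result. It does not by itself show how an individual patient's cost changes over time.
- **The test wording leaves room for a paired method.** A reader might infer that the plan prescribes only two-group tests and that its intervals are therefore wrong. The documents do not support that. A paired t-test or signed-rank test fits the stated wording, and no interval for the change is defined. A section after 9.7.1 and parts of Table 4 are redacted and may say more. An unpaired test would err on the conservative side.
- **This is a descriptive analysis under the third secondary objective.** With about 17,000 patients, some loss of precision matters little. That is right, and it makes the two biases the substance of the point.

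A reader might also infer that the comparison should be restricted to 36-month survivors. That would select on a later event and drop the costs of those who die. It answers a narrower question than the protocol's objective, which covers all incident patients.

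**Conclusion.** The point holds as one of confounding and incomplete specification. The comparison is within-patient, is made at each year's own prices, and keeps patients who die, so the estimated change cannot be read as change in cost alone. Price drift would add about 2% to 6% to year 3 against year 1 at an assumed 1% to 3% growth a year. Loss of sicker patients would take off about 3% to 13% under the simulated assumptions. The two act in opposite directions, and the protocol does not allow the net sign to be determined. Leaving the pairing open is a lesser matter: if an unpaired test were used, the standard error would be about 1.20 to 1.58 times too large, given the assumed correlations and equal SDs. The primary objective is unaffected. The change should be made before the cost analysis is run.

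**What to change.** In section 9.3.2.2 and the third-secondary row of Table 4, state the following for this comparison:

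1. Convert all costs to one price year, for example 2018, and keep the nominal result as a secondary display.
2. Keep all COPD-36 patients in the main result, with cost per observed patient-year defined as total cost divided by total patient-years in each year.
3. Use a paired or patient-clustered analysis, or a bootstrap that resamples whole patients with all their years, for the interval around the change.
4. Add a sensitivity analysis of within-patient differences (year 2 minus year 1, year 3 minus year 1) in patients alive at 36 months, with decedents reported separately.

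The cost is a few sentences, the choice of a published price index, and a little more programming. No further patient data are needed.

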
 Previous drug treatment in the pre-index period, based on appropriate ATC group level 
 Percentage of patients who received specific treatments (most common 10 treatments as observable for above samples) with at least two prescriptions in the pre-index period. 
Documentation referring to the 12 months follow-up after index date (for patient subgroups: 24 months/36 months follow-up, or complete follow-up period)
 
 For patients with available data resulting from a disease management program (DMP) 
 Weight [kg] (reported MIN, MAX and MEAN during follow-up period) Height [cm] Blood pressure (reported MIN, MAX and MEAN during follow-up period) Non-drug treatment recommendations Exacerbations (number and severity) FEV₁ (reported MIN, MAX and MEAN during follow-up period) Smoking status if applicable Drug treatment with long-acting bronchodilators (incl. separate reporting for respective agent classes beta-agonists, anticholinergics, methylxanthines) Drug treatment with short-acting agents Drug treatment with anti-inflammatory drugs (ICS, PDE-4, macrolides) Top-10 prescribed non-COPD drug therapies (based on ATC codes on appropriate level) 			

Name of company: Boehringer Ingelheim			
Name of finished medicinal product: COPD medication of any type			
Name of active ingredient: COPD medication of any type, ATC code R03			
Protocol date: 16 Oct 2019	Study number: 1237-0092	Version/Revision: 1.0	Version/Revision date: Not applicable

 • Antibiotics for systemic use (based on ATC J02AA) • Antibiotics in combination with corticosteroids (based on ATC D07C) • Systemic/oral corticosteroids (SCS/OCS; based on ATC R01AD02; D07AA01; D10AA02; H02AB04) • All-cause hospitalizations 
 ○ Among them: hospitalizations with COPD as main diagnosis (ICD-10 J44.-) • Among them: hospitalizations with a COPD exacerbation as main diagnosis (ICD-10 J44.1) • Exacerbations as documented by outpatient pneumologists (ICD-10 J44.1) • GP visits and pneumologists' visits and visits to other specialists • Prescription of COPD-associated aids 
 ○ Oxygen therapy • Date of death, if patient died during follow-up period (for censoring and time to event analyses). 			

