• Age	• Data about initial diagnoses including day of admission	• All physicians' visits including type of physician (esp. GPs and specialists in different specialist groups)	• Type of medication (medication number – in Germany: PZN), ATC code, number of packs, dates of prescription and of dispensing pharmacy	• Costs for outpatient devices/other supportive measures • Outpatient surgeries
• Gender	• All documented diagnoses/ procedures	• Documentation of diagnoses/ measures (EBM, GONr, OPS)	• Prescribing physician	• Other services paid by the insurance, e.g. salary co-payments etc. and Costs of other diagnostic/ therapeutic measures
• Type of insurance	• Length of stay in days	• Description of "safety" of diagnoses	• Medication-specific data (DDD, other information)	• Outpatient/in-patient long-term care data
• Partly: Socioeconomic status	• Costs including specific DRG	• Dates (physician visits; all diagnostic/ therapeutic measures)	• Costs; indirectly by calculation: patients' co-payments	• Days absent from work
• Mortality	• Data about inpatient/ outpatient rehabilitation clinic stays/other follow-up measures	• Costs of outpatient care based on activity points documented by doctors		• Partly DMP data: FEV ₁ , need for COPD medication, exacerbations (Suppl. Table 1)

For the claims data analysis, [REDACTED] will involve its university-affiliated partner, [REDACTED] has a longstanding experience in claims data analyses. [REDACTED] will close a contract with the cooperating sickness funds. This includes a detailed and mutually agreed list defining data extraction inclusion/exclusion criteria as well as all variables and formats to be used. Moreover, the contract outlines which data protection measures need to be implemented by [REDACTED]. The sickness funds will participate in the Steering Board of the study as well as being a co-author of all future publications of study results. The general model of cooperation is shown in Figure 2.

Figure 2

General study organization

In a first meeting of the Steering board, the study protocol draft will be discussed and, finally, be approved. After the approval of the steering board, the protocol will be submitted to the cooperating sickness funds and BI for final approval.

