Long-Term Oxygen Therapy (LTOT) ¹⁷	
• Number of patients who received LTOT• Mean/median time from incident COPD diagnosis until start of LTOT for those patients	
• Cost for LTOT

¹⁷ J96.1, Z99.0, Z99.1, Z99.8, Z99.9, Z46.8, Z46.9 (ICD-10-GM-2018); 8-712.1, 8-713.0, 8-716 (OPS 2016)

001-MCS-90-124_RD-01 (4.0)

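### Table 3 times the start of long-term oxygen therapy (LTOT) only among recipients inside fixed windows, and defines LTOT by codes although the plan elsewhere treats oxygen as a prescribed aid

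*Combined protocol and SAP*

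**What the plan says.** The LTOT row of Table 3 (section 9.3.2.2, third secondary outcome) has two resource-use items: "Number of patients who received LTOT" and "Mean/median time from incident COPD diagnosis until start of LTOT for those patients". A cost item for LTOT follows, without a source. The text above the table states that "HCRU and cost will be reported for the following samples in separate analyses: COPD-12, COPD-24, and COPD-36". Section 9.1 says that in selected analyses "incident COPD patients will be observed for an exact follow-up period of 12 months (in subgroup analyses: 24 and 36 months"), and that "censoring of patients will only be done in case a patient died during the respective follow-up period".

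Footnote 17 to Table 3 defines LTOT by codes: "J96.1, Z99.0, Z99.1, Z99.8, Z99.9, Z46.8, Z46.9 (ICD-10-GM-2018"), followed by three OPS 2016 procedure codes. The variable list in the abstract instead puts oxygen therapy under "Prescription of COPD-associated aids". Section 9.1 says that the dataset covers treatment with prescription aids, and Table 1 lists "Costs for outpatient devices/other supportive measures" in a column separate from diagnoses and procedures.

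The plan treats comparable questions differently. The note to Figure 3 assigns time-to-event analyses to the COPD-full data sample, and section 9.3.2.1 uses Kaplan-Meier there for time to dual and triple therapy.

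**The concern.** There are two linked problems in one row of the table.

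First, the timing summary is right-truncated. It uses only patients whose LTOT began before the window closed and ignores everyone who had not started or who died first. The same population then gives a very different figure in each sample merely because the window is longer. The abstract names early oxygen use among the outcomes to explore, and section 8 names LTOT in the resource-use objective. Resource use is also to be compared by DMP participation and by early triple therapy, and groups with quite different LTOT uptake could show almost the same recipient-only mean.

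Second, the plan points to two data sources for oxygen and does not say which one decides. Footnote 17 gives no rule on care setting, confirmed status or number of codes, whereas section 9.3.1 does so for comorbidities. Two programmers could therefore arrive at different recipients, start dates and costs.

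**Working it through.** **Timing.** The plan states no LTOT rate, hazard shape or expected time, so there is no figure to reproduce. The windows W = 12, 24 and 36 months come from section 9.3.2.2. All rates and shapes below are assumptions.

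For a constant monthly hazard λ, the mean among recipients is

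E[T | T ≤ W] = 1/λ − W·exp(−λW) / (1 − exp(−λW)).

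With 2% starting by 12 months, λ = −ln(0.98)/12, so 1/λ = 593.98 months:

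- W = 12: 593.98 − 12 × 0.98/0.02 = 593.98 − 588.00 = 5.98
- W = 24: 593.98 − 24 × 0.9604/0.0396 = 593.98 − 582.06 = 11.92
- W = 36: 593.98 − 36 × 0.941192/0.058808 = 593.98 − 576.16 = 17.82

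For Weibull hazards the mean is W minus the integral of F over (0, W) divided by F(W), done numerically. With a constant death hazard μ, λ in the formula becomes λ + μ.

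| Assumption | 12 mo | 24 mo | 36 mo | Share of W |
|---|---|---|---|---|
| Constant, 0.5% by 12 months | 5.99 | 11.98 | 17.95 | 0.50 |
| Constant, 2% | 5.98 | 11.92 | 17.82 | 0.50 |
| Constant, 20% | 5.78 | 11.11 | 16.01 | 0.44–0.48 |
| Constant, 2%, with 10% annual mortality | 5.87 | 11.50 | 16.87 | 0.47–0.49 |
| Weibull shape 0.3, 2% | 2.75 | 5.50 | 8.23 | 0.23 |
| Weibull shape 2, 2% | 7.98 | 15.87 | 23.56 | 0.65–0.67 |
| About half of 12-month recipients start at index | 2.96 | 7.87 | 13.23 | 0.25–0.37 |

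Three things follow.

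- The figure grows with the window under every assumption. From 12 to 36 months it rises by a factor of 17.82/5.98 = 2.98 at a constant 2%, 8.23/2.75 = 2.99 at shape 0.3, and 23.56/7.98 = 2.95 at shape 2.
- It barely registers uptake. With a constant hazard, 1% versus 4% starting by 12 months gives 36-month means of 17.91 and 17.63 months. The corresponding cumulative incidences are 1 − 0.99³ = 3.0% and 1 − 0.96³ = 11.5%.
- It does respond to the shape of the hazard: at 2%, the 12-month figure runs from 2.75 to 7.98 months.

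For comparison, cumulative incidence with death as competing event is λ/(λ + μ) × [1 − exp(−(λ + μ)W)]. At 2% LTOT and 10% annual mortality this is 1.9%, 3.6% and 5.1% at 12, 24 and 36 months.

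**Definition.** Set side by side:

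| Place | Source for oxygen |
|---|---|
| Abstract, variables | Prescribed aids |
| Section 9.1, text | Dataset includes prescription aids |
| Table 1, other data | Device costs |
| Table 3, footnote 17 | ICD-10-GM and OPS codes only |
| Table 3, LTOT cost | Source not stated |

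Other cost cells in Table 3 do name their basis: list prices for COPD drugs and treatment points for outpatient visits. A diagnosis code carries no device cost, so the code list cannot by itself supply the LTOT cost.

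**The case against.** A reader might infer that the statistic simply returns half the window. The documents do not support that. It needs a low, near-constant hazard, and no hazard is given. Early starts are plausible because a single hospital COPD diagnosis is enough to enter the cohort, and the assumed shapes span about 0.23 to 0.67 of W. Since the mean moves with shape, it carries some information on timing.

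Nor can one infer that LTOT incidence is lost. Table 3 reports the number of recipients. In samples with fixed follow-up where death is the only loss and patients who died are kept (footnote 11), recipients divided by sample size is the cumulative incidence at that horizon with death as competing event. This holds if membership of a sample depends on the index date and not on survival. What is missing is the percentage and the curve between the horizons.

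The windows also follow from the stated objective, and no comparison of LTOT timing across windows is planned. Parts of sections 9.3.2 and 9.7 and of Table 4 are redacted, including an endpoint named for Kaplan-Meier curves, so a time-to-event analysis of LTOT elsewhere cannot be excluded. It would not change the Table 3 row as it stands.

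On the codes, footnote 17 does not say that aid claims are excluded, and the two sources could be complementary. Nothing in the documents shows how far the codes misclassify LTOT, so a claim that they give wrong counts would be unsupported. A first oxygen-aid claim does not prove long-term use either. Finally, Table 1 is described as a first overview and does not show aid codes or supply dates, and the study extract still needs the fund's approval.

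**Conclusion.** The point holds in limited form. The recipient-only mean or median is right-truncated and driven mainly by window length: about half of it under an assumed low constant hazard, about 0.23 to 0.67 of it under the other shapes tried. It is a poor measure of early oxygen use and a weak basis for comparing groups. This rests on the visible wording of Table 3 and on assumed rates and shapes, since the plan gives none.

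The plan also gives two sources for oxygen therapy that must be reconciled, and its LTOT cost item has no matching source. The size of any resulting difference in counts or cost cannot be computed from the documents. The matter concerns one descriptive row of the third secondary outcome. It is worth correcting because LTOT is named in the objective and the correction is cheap.

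**What to change.** 1. Report LTOT timing as a cumulative incidence curve in COPD-FULL DATA with death as competing event, read at 12, 24 and 36 months. This follows the plan's own rule for time-to-event analyses. Patients still alive and without LTOT at the end of the data are censored there.
2. In COPD-12, COPD-24 and COPD-36, report LTOT recipients as a number and as a percentage of the sample.
3. If the recipient-only mean or median is kept, label it as conditional on starting within the window.
4. Define LTOT start and cost primarily from reimbursed oxygen-aid claims, subject to the fund delivering aid codes and supply dates, and state which claims count as long-term. Keep the footnote 17 list as a sensitivity definition, with a stated rule on setting, confirmed status and number of codes. Align the abstract, Table 3 and footnote 17.

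The cost is a few lines of text, a small amount of extra programming, and a check that aid-level fields are in the approved extract. If they are not, the code list has to serve as the main definition, and the plan should then say where the LTOT cost comes from.
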